4 INVESTIGATIONAL PLAN

4.1 Overall Study Design and Plan

This Phase 2, open-label, single-arm study is designed to evaluate the efficacy and safety of the combination of venetoclax and ibrutinib in Japanese subjects with R/R MCL.

Approximately 12 subjects will receive ibrutinib at 560 mg once daily and venetoclax starting at 20 mg once daily and gradually ramped up to a target dose of 400 mg once daily over a 5 week period.

Dose-limiting toxicities will be evaluated in the first 6 subjects, from Day 1 for a minimum of 5 weeks and at least 1 week of venetoclax dosing at 400 mg, in order to confirm the initial safety and tolerability in Japanese subjects. After the completion of the DLT evaluation period in the first 6 subjects, the AbbVie Study Team and investigators who enrolled the 6 treated subjects will review all available safety and PK data to evaluate the tolerability of venetoclax in combination with ibrutinib in Japanese subjects with R/R MCL. If there are zero or 1 DLTs in the first 6 subjects, enrolment of the additional 6 subjects will proceed. If DLTs are observed in 2 or more of the first 6 subjects, further enrollment in Japan will be interrupted and additional, a detailed safety assessment will be conducted. The Sponsor will consult the Independent Safety Monitor (ISM) with results of the safety evaluation and Sponsor's conclusion on tolerability, then receive the answer from ISM.

To mitigate the risk of TLS, a ramp-up period of approximately 5 weeks will be employed with a stepwise increase of the venetoclax dose ([Figure 1](#)). Subjects will receive a venetoclax dose of 20 mg on Week 1 Day 1 of the ramp-up period and continue with dose increases every 7 days as tolerated. Ramp-up doses of venetoclax include 20 mg, 50 mg, 100 mg, 200 mg, and 400 mg. Subjects will receive ibrutinib at 560 mg once daily starting on Week 1 Day 1.

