If one or more electrolyte changes suggestive of TLS occur within 24 hours of the 20 mg dose, no additional venetoclax doses will be administered until resolution. If correction of electrolytes abnormalities is performed, the subsequent dose of venetoclax can only be given when electrolytes have been stable without any more treatment for at least 24 hours. Refer to [Table 2](#), Recommended Dose Modifications for Venetoclax-Related Toxicities, for additional TLS management guidelines. Upon resolution of laboratory abnormalities, the subject will resume at the ramp-up dose. When venetoclax dose interruptions are required during the ramp-up period, the next highest dose level may be initiated 7 days from the start of the current dose level, once the toxicity has resolved to Grade 1 or baseline level and at the investigator's discretion. At the investigator's discretion, the duration of a single dose level during the ramp-up period may be longer than 7 days before increasing to the next highest dose level.

For all ramp-up doses, laboratory values for subject management must be reviewed in real time by the investigator or designee, and prior to the subject's next dose, to ensure appropriate subject management. Based on the laboratory values, the subject may continue dosing, may need to hold dose until resolution, may require hospitalization for further monitoring, or may need additional post-dose laboratory checks.

Initially, subjects at high-risk for TLS will be hospitalized at the start of the venetoclax 20 mg ramp-up dose and again at the start of the 50 mg ramp-up dose for monitoring and prophylaxis of TLS. Subjects will be considered as high-risk for TLS if they have a high tumor burden (at least one lesion > 10 cm; or at least one lesion > 5 cm and circulating lymphocytes > 25,000 cells/mm³) and/or with baseline creatinine clearance (CrCl) < 60 mL/min. Subjects not meeting the high-risk criteria will be considered low risk for TLS. Subjects will be discharged from hospital if there is no evidence of TLS. AbbVie will review the safety data during the course of the study to determine whether continued hospitalization of subjects at high-risk for TLS during ramp-up remains warranted.

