6.2 Toxicity Management

Venetoclax

Dose Modification for Adverse Reactions

Venetoclax dosing interruption and/or dose reduction may be required. See [Table 2](#) for dose modifications for hematologic and other toxicities related to venetoclax. For subjects who have had a dosing interruption greater than 1 week during the ramp-up period or greater than 2 weeks when at target dose, reassess for risk of TLS to determine if re-initiation with a reduced dose is necessary. Venetoclax dose reduction is not allowed during the DLT assessment period.

Table 2. Recommended Dose Modifications for Venetoclax-Related Toxicities

Event	Occurrence	Action
Tumor Lysis Syndrome Blood chemistry changes or symptoms suggestive of TLS	Any	Withhold the next day's dose. If resolved within 24 to 48 hours of last dose, once the toxicity has resolved to Grade 1 or baseline level, resume at the same dose.
		For any blood chemistry changes requiring more than 48 hours to resolve, once the toxicity has resolved to Grade 1 or baseline level, resume at a reduced dose ^a (see Table 3)
		For any events of clinical TLS, once the toxicity has resolved to Grade 1 or baseline level, resume at a reduced dose following resolution (see Table 3)
Non-Hematologic Toxicities Grade 3 or 4 non-hematologic toxicities	First	Interrupt venetoclax Once the toxicity has resolved to Grade 1 or baseline level, venetoclax therapy may be resumed at the same dose. No dose modification is required.
	Second and subsequent	Interrupt venetoclax Once the toxicity has resolved to Grade 1 or baseline level, resume at a reduced dose following resolution (see Table 3). A larger dose reduction may occur at the discretion of the investigator.
Hematologic Toxicities Grade 3 or 4 neutropenia with infection or fever; or Grade 4 hematologic toxicities (except lymphopenia)	First	Interrupt venetoclax. To reduce the infection risks associated with neutropenia, G-CSF may be administered with venetoclax if clinically indicated. Once the toxicity has resolved to Grade 1 or baseline level, venetoclax may be resumed at the same dose. ^a
	Second and subsequent occurrence	Interrupt venetoclax. Consider using G-CSF as clinically indicated. Once the toxicity has resolved to Grade 1 or baseline level, resume at a reduced dose following resolution ^a (see Table 3). A larger dose reduction may occur at the discretion of the investigator.

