DLT = dose limiting toxicity; G-CSF = granulocyte-colony stimulating factor; TLS = tumor lysis syndrome

a. Venetoclax dose reduction is not allowed during the DLT assessment period.

Consider discontinuing venetoclax for subjects who require dose reductions to less than 100 mg for more than 2 weeks.

If the dose of venetoclax is reduced, at the investigator's discretion, the dose of venetoclax may be re-escalated after 2 months of a dose reduction in the absence of a recurrence of the toxicity that led to the reduction. Subsequent dose re-escalations should be discussed with the AbbVie TA MD.

Table 3. Dose Modification for Toxicity During Venetoclax Treatment

Dose at Interruption	Restart Dose ^a
400 mg	300 mg
300 mg	200 mg
200 mg	100 mg

a. Continue the reduced dose for at least 1 week before increasing the dose.

Prophylaxis and Management of Tumor Lysis Syndrome

Venetoclax can cause rapid reduction in tumor and thus poses a risk for TLS in the ramp-up period. Changes in electrolytes consistent with TLS that require prompt management can occur as early as 6 to 8 hours following the first dose of venetoclax and at each dose increase. The risk of TLS is a continuum based on multiple factors, including comorbidities. Subjects with high tumor burden are at greater risk of TLS when initiating venetoclax. Reduced renal function further increases the risk. The risk may decrease as tumor burden decreases with continued venetoclax treatment.

Tumor burden assessments, including radiographic evaluation (e.g., CT scan) should be performed at Screening as well as blood chemistry assessments (potassium, phosphorus, calcium, uric acid, creatinine, lactate dehydrogenase, and, if available, albumin, corrected calcium, and ionized calcium) in all subjects. Pre-existing abnormalities should be corrected prior to initiation of treatment with venetoclax.

- High risk for TLS: Subjects with high tumor burden (at least one lesion > 10 cm; or at least one lesion > 5 cm **and** circulating lymphocytes > 25,000 cells/mm³) and/or with baseline CrCl < 60 mL/min.
- Low risk for TLS: Subjects not meeting the criteria described above.

The prophylaxis measures listed below should be followed and more intensive measures (including hospitalization) should be employed for subjects at high-risk for TLS based on local guidelines or institutional standards:

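### Protocol 6.2 is inconsistent on when a venetoclax dose reduced for toxicity may be increased: after 2 months without recurrence in the text, against a floor of only 1 week in Table 3 footnote a

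*Protocol*

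**What the plan says.** Both statements stand in Protocol Section 6.2, a few lines apart.

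- The text between Tables 2 and 3 says that a reduced venetoclax dose, at the investigator's discretion, "may be re-escalated after 2 months of a dose reduction in the absence of a recurrence of the toxicity that led to the reduction". It adds that later re-escalations should be discussed with the sponsor's medical director.
- Footnote a, attached to the restart-dose column of Table 3, says: "Continue the reduced dose for at least 1 week before increasing the dose". It mentions neither recurrence nor consultation.

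Table 3 is titled "Table 3. Dose Modification for Toxicity During Venetoclax Treatment". Its rows run from 400 to 300 mg, 300 to 200 mg and 200 to 100 mg. Table 2 refers to it for tumor lysis syndrome (TLS) that is clinical or slow to resolve, and for repeat severe non-hematologic or hematologic toxicity. The instruction for repeat non-hematologic toxicity is typical: "resume at a reduced dose following resolution (see Table 3). A larger dose reduction may occur at the discretion of the investigator".

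**The concern.** A site that has restarted a subject at a reduced dose finds two statements about how long to stay there. They differ in length, and only the text makes the increase depend on the toxicity not having come back. Neither says whether it belongs to ramp-up, to the target-dose period or to a particular toxicity, and neither is given precedence.

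Three things are at stake:

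- **Safety.** These reductions follow TLS or recurrent severe toxicity, so the interval governs re-exposure to the higher dose.
- **Deviations.** SAP Appendix A lists subjects who received an incorrect dose. Whether an increase in week 2 belongs on that list depends on which sentence is applied.
- **Exposure.** SAP Section 6.0 reports relative dose intensity, whose value moves with the time spent at the lower dose.

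**Working it through.** There is no statistical figure in the plan to reproduce here. The check sets the passages side by side and then does some day and dose arithmetic.

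**Do both sentences cover the same reductions?** The text applies whenever the venetoclax dose is reduced. The footnote applies to the restart doses in Table 3, which is where Table 2 sends toxicity reductions. A subject restarted at 300 mg after an interruption at 400 mg therefore falls under both as written.

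**Could the footnote be meant for ramp-up only?** The documents do not say so, and several features fit poorly:

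- The Table 3 title covers venetoclax treatment in general.
- Protocol Section 4.1 lists the ramp-up levels: "Ramp-up doses of venetoclax include 20 mg, 50 mg, 100 mg, 200 mg, and 400 mg". The 300 mg level in Table 3 is not among them.
- Table 3 gives no restart dose for interruptions at 20, 50 or 100 mg, three of the five ramp-up levels.
- Section 4.1 already has its own rule for ramp-up interruptions: "the next highest dose level may be initiated 7 days from the start of the current dose level".
- Elsewhere in Section 6.2, where an interval differs between ramp-up and target dose (the length of interruption that triggers a new TLS risk assessment), the protocol names the phase.
- Section 6.2 bars venetoclax reduction during the assessment period for dose-limiting toxicity, which includes at least 1 week at 400 mg. For those subjects, a Table 3 reduction comes only after the target dose has been reached.

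**Width of the gap**

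- Footnote: 1 week = 7 days.
- Text: 2 calendar months = 59 to 62 days, or 56 days if read as 8 weeks.
- Difference: 56 − 7 = 49 days, up to 62 − 7 = 55 days.
- Ratio: 56 / 7 = 8.0, up to 62 / 7 = 8.9.

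**Effect on relative dose intensity.** SAP Section 6.0 defines it as observed over planned dose intensity, with the planned value averaged over the 104-week maximum. Assume 7 days per ramp-up step, and one 400-to-300 mg reduction that is later reversed in a subject who takes venetoclax for the full 104 weeks.

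- Duration: 104 × 7 = 728 days.
- Planned total: (20 + 50 + 100 + 200) × 7 + 400 × (728 − 28) = 2,590 + 280,000 = 282,590 mg.
- Dose forgone by the longer wait: 49 × 100 = 4,900 mg, up to 55 × 100 = 5,500 mg.
- Shift: 4,900 / 282,590 = 1.7 percentage points, up to 5,500 / 282,590 = 1.9 percentage points.

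The observed intensity divides by actual duration, so the same step weighs more in a subject treated for less time. At 52 weeks (364 days), the shift is twice as large, about 3.5 to 3.9 points.

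**The case against.** The strongest reply is that the sentences do not truly collide. The footnote grants nothing; it only sets a floor. The permission to increase comes from the text, and a site that waits 2 months complies with both. This stands. A reader might infer that the footnote authorizes an increase after 1 week, but its wording does not support that. What the reply leaves open is the interval in between. The documents do not say that the text prevails, and a floor of 1 week has no evident purpose if no increase is allowed before 2 months.

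A second reply is a phase-based reading: the 1-week minimum belongs to stepping up during ramp-up, and the 2 months to returning to target dose. This is possible, and the 7-day ramp-up steps lend it some support. It is nowhere stated, however, and fits poorly for the reasons given in the check.

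A third reply points to safeguards. Table 2 requires resolution to Grade 1 or baseline before any restart, whichever sentence is followed. The text adds investigator discretion, absence of recurrence and consultation for later re-escalations. These soften the safety concern, but the conditions in the text are not carried into the footnote.

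Two stronger inferences are also tempting, and the documents support neither. One is that every restart in Table 3 is in doubt. The restart doses are unambiguous; only the timing of a later, optional increase is unclear. The other is that the SAP's dose-reduction summaries depend on the sentence followed. The SAP counts occurrences of reduction, and the timing of a later increase does not directly change a count already made.

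**Conclusion.** The inconsistency is real but limited. For a venetoclax dose reduced for toxicity, the text places the earliest increase at 2 months without recurrence, while the footnote bounds it only at 1 week and carries no such condition. An increase in the intervening 49 to 55 days is consistent with one and too early under the other. This rests on reading both sentences without a phase restriction, since none is stated, and on taking the text's 2 months as the earliest time for an increase, which is its natural sense although it contains no explicit prohibition.

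The consequences are for safety after a toxicity-driven reduction, for the classification of dosing deviations and, modestly, for relative dose intensity. The definition of dose intensity is sound; only its value in re-escalated subjects moves. The sample size, the primary test and its type I error are not touched.

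The practical reach may be small. About 12 subjects are planned, venetoclax lasts at most 104 weeks, and Protocol Appendix J records that the primary analysis is complete. The documents do not say how many subjects were reduced or still take venetoclax.

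**What to change.** Reconcile the text and footnote a in Protocol Section 6.2. Either state a single rule, or state the scope of each sentence (phase, type of toxicity) and whether the non-recurrence condition applies to both. The clinical team decides the interval; this review takes no view on it. The cost is one sentence or one footnote.

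If no subject still takes venetoclax, an amendment would serve little purpose. The study report should then state which rule sites applied and on what basis an early increase was or was not listed as a dosing deviation.

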6.3 Dose-Limiting Toxicity Criteria

Tolerability in the first 6 Japanese subjects (DLT assessment period) will be determined considering all available data, including information on AEs, laboratory results, and PK data. For each of the first 6 subjects, DLTs will be assessed during the venetoclax ramp-up period for a minimum of 5 weeks and at least 1 week of venetoclax dosing at 400 mg.

A DLT is defined as any Grade ≥ 3 AE considered to be at least possibly related to study drug (ibrutinib and/or venetoclax) and occurring during the DLT assessment period with the following clarifications:

Non-Hematologic DLTs:

- Grade ≥ 3 nausea, vomiting, or diarrhea, uncontrolled despite maximum medical supportive care and persisting > 5 days
- Grade 3 fatigue persisting > 7 days
- Grade 3 infection is not a DLT; however, an infection with life-threatening consequences or requiring urgent intervention (Grade 4) will be considered a DLT
- Treatment delay of any study drug of > 7 consecutive days for toxicity.

Hematologic DLTs:

- Grade 3 neutropenia is not a DLT; however, Grade 4 neutropenia ($ANC < 500/\text{mm}^3$) lasting for > 7 days is a DLT
- Grade 3 or 4 neutropenia complicated by fever $\geq 38.5^\circ\text{C}$ or infection
- Grade 4 thrombocytopenia ($< 25,000/\text{mm}^3$) that persists for > 7 days
- Grade 3 or 4 thrombocytopenia associated with Grade 2 or greater bleeding
- Grade 3 anemia is not a DLT; however, Grade 4 anemia is a DLT
- Treatment delay of any study drug > 7 consecutive days for hematologic toxicity.

In addition, clinically important or persistent toxicities that are not included in the above criteria will be considered a DLT following review by the Sponsor and the investigators.

Subjects who miss $\geq 20\%$ of the planned doses of venetoclax or ibrutinib for reasons other than toxicity (e.g., non-compliance, withdrawal of consent, disease progression) during the DLT assessment period, or subjects who do not complete the DLT assessment period for any reason other than a DLT will be considered non-evaluable and will need to be replaced.

A subject must be on study from Day 1 for a minimum of 5 weeks and at least 1 week of venetoclax dosing at 400 mg to be evaluable for DLT assessment. However, in circumstances of an event not related to study drug (e.g., traffic accident, clear disease progression) that leads to study discontinuation before the end of the defined DLT assessment period, the subject might be deemed evaluable if the Sponsor and investigators and agree.

Subjects who are replaced for DLT assessments are also included in the planned total 12 subjects.

Enrollment of subjects will be suspended after the first 6 subjects are enrolled for DLT assessment. The decision around tolerability will be based on data from all subjects who received at least 1 dose of the study drug, regardless of whether the subjects are DLT evaluable or not.

Evaluation of Tolerability:

Dose-limiting toxicities will be evaluated in the first 6 subjects from the planned total of 12 subjects in order to confirm the initial safety and tolerability in Japanese subjects. Enrollment of new subjects will be suspended once the first 6 subjects evaluable for tolerability are enrolled. Dose-limiting toxicities will be evaluated during the venetoclax ramp-up period, from Day 1 for a minimum of 5 weeks and at least 1 week of venetoclax dosing at 400 mg. After the completion of the DLT evaluation period in the first 6 subjects, the AbbVie Study Team and investigators who enrolled the treated subjects will review all available safety and PK data to evaluate whether venetoclax in combination with ibrutinib is tolerable in Japanese subjects with R/R MCL. If there is 0 or 1 DLT in the first 6 subjects, enrolment of the additional 6 subjects will proceed. If DLTs are observed in 2 or more of the first 6 subjects, further enrollment will be interrupted and additional, detailed safety assessment will be conducted, including discussions to determine if other doses should be explored. The Sponsor will consult the ISM with the results of safety evaluation and the Sponsor's conclusion on tolerability, then receive the response from the ISM.

7 STATISTICAL METHODS & DETERMINATION OF SAMPLE SIZE

7.1 Statistical and Analytical Plans

The statistical methods provided in this protocol will be utilized for primary and secondary analyses. Complete and specific details of the statistical analysis will be described in the Statistical Analysis Plan (SAP).

The primary analysis will be conducted after the last subject has completed the Week 13 disease assessments or all subjects have discontinued the study, whichever is earlier.

In the DLT assessment period, the first 6 study subjects enrolled will be evaluated for the tolerability of the venetoclax and ibrutinib combination for a minimum of 5 weeks and at least 1 week of venetoclax dosing at 400 mg.

7.2 Definition for Analysis Populations

The full analysis set (FAS) includes all subjects who received at least 1 dose of study drug. The FAS will be used for all efficacy (except the endpoints based on IRC assessment), safety, pharmacokinetic, and baseline analyses. The per protocol (PP) population excludes FAS subjects who have been determined as non-evaluable disease at baseline based on IRC assessment. For endpoints based on IRC assessment, PP population will be used. For investigator assessed endpoints, PP population may be used as appropriate.

Statistical Analyses for Efficacy

Summary and Analysis of the Primary Endpoint

The primary efficacy endpoint will be the best overall response of CR (defined as achieving complete metabolic and/or radiologic response at any time point during the study), according to the Revised Criteria for Response Assessment as assessed by the IRC²⁸ in the PP population. The primary endpoint will be evaluated using complete response rate (CRR), defined as the proportion of subjects achieving a best overall response of CR for the venetoclax and ibrutinib combination in the PP population, and will be compared to the threshold CRR of 12.5% using the exact binomial test at a 1-sided overall significance level of 0.025. The CRR will be estimated using exact binomial distribution, the estimate and 95% CI for CRR will be constructed.

Subjects who are enrolled but have no disease assessment post-baseline will be considered as non-responders in the calculation of CRR.

Summary and Analysis of Secondary Endpoints

The secondary efficacy analysis will be based on the following endpoints:

- Best overall response of CR by investigator

- Best overall response of CR or PR (defined as achieving partial metabolic and/or radiologic response at any time point during the study), DOR, and undetectable MRD, as assessed by investigator and IRC, respectively.
- PFS by investigator
- OS

The same methodology as for the analysis of CR assessed by IRC will be applied to the analysis of CR assessed by investigator.

Endpoint of best overall response of CR or PR will be evaluated using ORR. The ORR will be defined as the proportion of subjects with a best overall response of CR or PR, according to the Revised Criteria for Response Assessment as assessed by the investigator.²⁸ The estimate and 95% CI for ORR based on exact binomial distribution will be constructed. Similarly, analysis of ORR assessed by IRC will be performed.

DOR will be defined as the time from the first occurrence of response to disease progression or death, whichever occurs first, according to the Revised Criteria for Response Assessment as assessed by the investigator.²⁸ If a subject is still responding, subjects will be censored at the date of the last adequate disease assessment. DOR will be analyzed for subjects who achieve a best overall response of CR/PR. The distribution of the DOR will be estimated using Kaplan-Meier methodology. If estimable, median DOR and the corresponding 95% CI will be provided. Similarly, analysis of DOR will be performed using IRC-assessed data.

Minimal residual disease (MRD) rate will be defined as the proportion of subjects with undetectable MRD who achieve a best overall response of CR, according to the Revised Criteria for Response Assessment as assessed by the investigator²⁸ will be estimated and the corresponding 95% CI for the proportion based on exact binomial distribution will be constructed. Similarly, analysis of the proportion of subjects with undetectable MRD who achieve a best overall response of CR, as assessed by the IRC, will be estimated.

Progression-free survival will be defined as the time from the date of the first dose of any study drug (venetoclax or ibrutinib) to the date of investigator-assessed disease progression, using the Revised Response Criteria for Response Assessment,²⁸ or death from any cause, whichever occurs first. All events of disease progression will be included, regardless of whether the event occurred while the subject was still taking study drug or after the subject discontinued study drug. If the subject does not experience disease progression or death, then the data will be censored at the date of the last adequate disease assessment. Data for subjects without any disease assessments performed after the baseline visit will be censored at the date of the first dose. The distribution of the PFS events will be estimated using Kaplan-Meier methodology. If estimable, median PFS and the corresponding 95% CI will be provided.

Overall survival will be defined as the time from the date of the first dose of any study drug (venetoclax or ibrutinib) to death from any cause. All events of death will be included, regardless of whether the event occurred while the subject was still taking study drug or after the subject discontinued study drug. If a subject has not died, then the data will be censored at the date the subject was last known to be alive. The distribution of the OS will be estimated using Kaplan-Meier methodology. If estimable, median OS and the corresponding 95% CI will be provided.

Details on the secondary efficacy analyses are provided in the SAP.

Summary and Analysis of Additional Efficacy Endpoints

Details on other efficacy analyses are provided in the SAP.

Subgroup Analysis for Efficacy

There is no separate subgroup analysis planned for this study.

